#### 4.4 Study Days

For the purpose of the analysis, study day will be calculated relative to first administration of the study drug. Specifically:

If visit date is prior to dosing:

Study day = date of visit - first dose date

If visit date is on or after dosing:

Study day = date of visit – first dose date + 1.

Statistical analyses will be performed using study day as defined above.

CONFIDENTIAL Page 13 of 28

# 4.5 Handling of Dropouts or Missing Data

If laboratory result is below detection limit, it will be imputed to half of detection limit in table and figure. The result will be listed as is in listings.

### 4.6 Multiple Comparisons

No multiple comparisons will be performed.

#### 4.7 Data Derivations and Transformations

No data derivations or transformations will be performed.

#### 5. STUDY SUBJECTS

### 5.1 Disposition of Subjects

Enrollment, screen failure, major protocol violations, and discontinuations from the study will be summarized by treatment cohort. The number of subjects who were enrolled, dosed, discontinued, and completed the study will be summarized.

#### **5.2** Protocol Deviations

Distribution for the types of major protocol deviations and the number of subjects that deviate from the protocol will be tabulated for the dose cohorts. Also, the number and percent of subjects with a protocol deviation related to COVID-19 will be summarized. A by-subject listing will also be provided. Protocol deviations related to COVID-19 will be flagged in the listing.

# 5.3 Demographic Characteristics

Demographic characteristics, including age, sex, race, and ethnicity, will be summarized using means, standard deviations, medians, and ranges for continuous variables, and proportions for categorical variables. All summaries will be presented overall and by treatment cohort for the Safety Analysis Set. A by-subject listing will also be provided.

#### **5.4** Baseline Characteristics

Baseline characteristics including, height, weight, FVC, 6MWT, urine GAG, and IDS, will be summarized using means, standard deviations, medians, and ranges for continuous variables, and proportions for categorical variables. All summaries will be presented overall and by treatment cohort for the Safety Analysis Set. A by-subject listing will also be provided.

# 5.5 Medical History and Historical Surgeries and Procedures

All past and/or concomitant diseases and past surgical procedures will be classified by system organ class (SOC) and preferred term (PT) using the Medical Dictionary for Regulatory Activities (MedDRA version 23.0). The number and percent of subjects with each medical condition and surgical procedure will be presented for each SOC and PT for the Safety Analysis Set overall and by dose cohorts. A by-subject listing will also be provided.

CONFIDENTIAL Page 14 of 28

#### 5.6 Concomitant Medications and Supportive Care

Concomitant medications and supportive care will be coded using World Health Organization (WHO) drug classifications version B2 enhanced September 2017. The number and percent of safety subjects using concomitant medications will be tabulated by default Anatomical, Therapeutic, and Chemical (ATC) classification Level 4 and by preferred name for the Safety Analysis Set overall and by dose cohorts. A by-subject listing will also be provided.

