	Liver function tests (aspartate aminotransferase [AST], alanine aminotransferase [ALT], total and direct bilirubin, alkaline phosphatase, lactate dehydrogenase (LDH), albumin, and total protein levels) will be conducted for evaluation of AAV-mediated immunogenicity twice a week during the first 20 weeks after SB-913 infusion and may be conducted at home if the subject is remote. Blood samples for liver function tests will be drawn 2-4 days apart when possible, except for the first week when they will be drawn on the Day 1 and Day 7 visits. Liver function tests will subsequently be conducted at all study visits. If, in spite of pretreatment with prednisone or equivalent corticosteroid, there is evidence of transaminitis, the dose of prednisone or equivalent corticosteroid will be increased on a case-by-case basis, and liver function will be assessed twice a week until normalization of liver enzymes, and then per protocol thereafter
Dose Escalation	Within each cohort, treatment will be staggered so that each subsequent subject will not be infused until the preceding subject has been observed for at least 4 weeks.
	Dose escalation to the next cohort will not occur until at least 4 weeks after the last subject in the preceding cohort has been dosed and the safety data from the prior cohort has been reviewed by the SMC and the SMC has agreed to dose escalate.
	Dosing and dose escalation will be paused if a Grade 3 or higher AE occurs, or if two Grade 2 AEs occur within the same organ class and persist for more than 2 weeks with therapy, provided these AEs are not related to the primary MPS II disease or treatment of the MPS II disease. In such an event, the SMC will be convened to assess for potential dose-limiting toxicity (DLT) and to provide recommendations on whether to expand the cohort at the same dose level, to dose de-escalate, or to continue the study as planned (refer to the Stopping Rules).

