3.5 Study Schedule

Subjects who satisfy all eligibility criteria will be enrolled into one of the following treatment cohorts:

Cohort #	Age Range (y)	Total Dose (vg/kg)	# Subjects
1	≥18	5.00E+12	2
2	≥18	1.00E+13	2
3	≥18	5.00E+13	2
4	≥18	1.20E+14	2
5	12-17	5.00E+13	2
6	12-17	TBD	2
7	5-11	TBD	2
8	5-11	TBD	2

Two subjects will be enrolled in each cohort, and will be dosed at least 4 weeks apart. SMC review occurs after at least 4 weeks of safety data is available from 2 subjects in each cohort.

The pediatric cohorts will be enrolled only after review of cumulative adult safety data by the SMC (see Section 12.3). The starting dose for pediatric cohorts 6 through 8 will be decided based on SMC review of study data, and must meet pre-defined safety criteria (see Pediatric Dosing).

Approximately 2 additional subjects may be added to any age cohort after SMC review of study data if safety criteria are met (see Safety Monitoring Committee), with up to a total of 32 subjects in the study.

TBD, to be determined based on SMC Review *will be enrolled if dose adjustment is indicated after SMC Review of study data

Figure 10. Schema of Cohort Enrollment.

Blue box = adult subjects age \geq 18 years; purple box = pediatric subjects age 12-17; green box = pediatric subjects age 5-11; orange box = SMC review; dashed orange line = SMC recommendation on pediatric dosing.

Subjects who received ERT prior to study enrollment will continue to receive ERT during the study and remain on their current schedule per standard of care unless they undergo ERT withdrawal (see Section 11.4). However, ERT will be omitted during the week of the SB-913 infusion to facilitate accurate baseline testing (e.g.; of GAG levels in urine, blood, and of IDS activity in blood) and to allow a week free of ERT after the SB-913 infusion.

To minimize the potential immune response to the AAV capsid protein, the engineered ZFNs, or the endogenous IDS, and to preserve hepatic function, prednisone or equivalent corticosteroid will be administered prophylactically starting 2 days prior to SB-913 infusion and will be tapered over a period of approximately 20 weeks (see Appendix 3).

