4.2 Exclusion Criteria

Subjects who meet any of the following criteria will be excluded from participating in the study:

- 1. Known to be unresponsive to ERT.
- 2. Neutralizing antibodies in serum (immune response) to AAV2/6.
- 3. Serious intercurrent illness or clinically significant organic disease (unless secondary to MPS II) such as cardiovascular, hepatic, pulmonary, neurologic, or renal disease.
- 4. Receiving antiviral therapy for hepatitis B or C, or with active hepatitis B (HBV DNA positive or HBV surface antigen positive) or hepatitis C (HCV RNA viral load) or human immunodeficiency virus (HIV)-1/2 (HIV RNA viral load or HIV antibody positive); to be considered negative for hepatitis C after treatment of an active HCV infection, viral assays in 2 samples collected at least 6 months apart must be negative.
- 5. Lack of tolerance to idursulfase treatment with significant infusion-associated reactions (IARs) or occurrence of anaphylaxis.
- 6. Polymorphisms in the ZFN-targeted region of the albumin locus.
- 7. Liver fibrosis score of 3 or 4 on a 0 to 4 point scale (Desmet et al. 1994) if subject has had a liver biopsy within 2 years of Screening.
- 8. Markers of hepatic dysfunction as evidenced by one or more of the following:
 - a) Platelet count $<100,000/\mu$ L

- b) Albumin $\leq 3.2 \text{ g/dL}$
- c) Total bilirubin >1.5 x upper limit of normal (ULN) and direct bilirubin ≥0.5 mg/dL
- d) Alkaline phosphatase >2.0 x ULN
- e) ALT or AST > 2.0 x ULN
- 9. Creatinine $\geq 1.5 \text{ mg/dL}$.
- 10. Weight < 20 kg at Screening visit.
- 11. Pregnant or breastfeeding female.
- 12. Contraindication to the use of corticosteroids.
- 13. Current treatment with systemic (IV or oral) immunomodulatory agent or steroid use (topical treatment allowed, e.g., for asthma or eczema).
- 14. History of active malignancy in past 5 years (non-melanoma skin cancer or cervical cancer *in situ* permitted).
- 15. Participation in prior investigational drug or medical device study within the previous 3 months.
- 16. Prior treatment with a gene therapy product.
- 17. History of alcohol or substance abuse that in the opinion of the Principal Investigator may interfere with study compliance.
- 18. History of therapeutic non-adherence.
- 19. Elevated or abnormal circulating α -fetoprotein (AFP).
- 20. Any other reason that, in the opinion of the Principal Investigator or Medical Monitor, would render the subject unsuitable for participation in the study.

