7.2 Concomitant Medication and Supportive Care

The Principal Investigator will record all concomitant medications, including over-the-counter medicinal products, dietary supplements, herbal medications, and medications given in treatment of AEs, taken by a subject from Screening throughout the course of the study on the concomitant medications page in the subject's case report form (CRF).

Subjects who received ERT prior to study enrollment should continue to receive ERT during the study as per standard of care unless they undergo ERT withdrawal (see Section 11.4), except during the week of the SB-913 infusion, and such treatment should be recorded on the concomitant medications page.

Treatment with prednisone or equivalent corticosteroid and pre-treatment with acetaminophen (Tylenol or Paracetamol) and diphenhydramine hydrochloride or equivalent medication should also be recorded on the concomitant medications page.

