APPENDIX 3: IMMUNOSUPPRESSION REGIMEN

Prednisone or equivalent corticosteroid regimen is commenced 2 days prior to Day 0 of SB-913 infusion and given once daily unless otherwise stated. Subject's liver function will be monitored twice a week while on prednisone or equivalent corticosteroid. Blood for liver panel shall be drawn 2-4 days apart when possible, except for the first week when it will be drawn on the Day 1 and Day 7 visits. Tapering of prednisone or equivalent corticosteroid will only proceed if ALT/AST activity levels are stable or declining (based on the 2 assessments of the preceding week).

If subjects develop increased ALT > 2 fold Baseline while on prednisone or equivalent corticosteroid or after stopping prednisone or equivalent corticosteroid, the prednisone or equivalent corticosteroid regimen may be adjusted or restarted at the Principal Investigator's discretion after consultation with the Medical Monitor. Twice a week liver panel testing should continue until the prednisone or equivalent corticosteroid course has been terminated.

An ACTH stimulation (cosyntropin) test will be performed prior to the first prednisone or equivalent corticosteroid dose and again during Week 20 or at the end of the scheduled taper to ensure that the adrenal cortical function has not been suppressed. Should prednisone or equivalent corticosteroid treatment be repeated due to increased transaminase activity, the ACTH stimulation test will be repeated at the end of taper at the Principal Investigator's discretion.

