# 7.1 Extent of Exposure

The expected and actual dose of SB-913, and the reasons for infusion interruption will be summarized and presented in a table.

A listing will also be provided.

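### The corticosteroid any-use count is about 100% in every cohort by design, and no planned table shows steroid increase, prolongation or restart by dose cohort

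*SAP*

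**What the plan says.** Protocol 3.5 states that "prednisone or equivalent corticosteroid will be administered prophylactically starting 2 days prior to SB-913 infusion", with a taper over about 20 weeks. Protocol 4.2 excludes anyone with a "Contraindication to the use of corticosteroids". If transaminitis appears despite this, Protocol 3.5 says that "the dose of prednisone or equivalent corticosteroid will be increased on a case-by-case basis". Appendix 3 lets the taper proceed only while ALT and AST are stable or falling, and says that above twice the Baseline ALT the "regimen may be adjusted or restarted".

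Protocol 7.2 places the steroid with the other concomitant drugs: "Treatment with prednisone or equivalent corticosteroid and pre-treatment with acetaminophen" and an antihistamine are to be recorded on the concomitant medications page. SAP 5.6 then gives the only summary of that page: "The number and percent of safety subjects using concomitant medications will be tabulated by default Anatomical, Therapeutic, and Chemical (ATC) classification Level 4", with a further split by drug name, both overall and within each dose cohort. It adds: "A by-subject listing will also be provided".

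The exposure section, SAP 7.1, concerns the vector alone: "The expected and actual dose of SB-913, and the reasons for infusion interruption will be summarized".

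**The concern.** Transaminitis is the first key anticipated risk in Protocol 12.2. Steroid dose both responds to ALT and is meant to bring it down, so ALT by dose is hard to interpret without steroid by dose. If a higher vector dose provoked more liver inflammation and that was contained with more steroid, by-visit ALT summaries could look similar across cohorts, and the steroid row would not reveal the difference.

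The SAP's own aims make this relevant. SAP 2.2.1 names concomitant medications among the safety evaluations, and SAP 4 says the displays are meant to describe how safety varies by dose. A count that is constant by design cannot do that for the drug used to manage the main expected toxicity. Steroid exposure also carries its own risks: Protocol 8.2 lists 16 adverse reactions to glucocorticoids.

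**Working it through.** The study is descriptive, so there is no power or alpha figure to reproduce. The check has four parts.

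**1. Does any planned table show off-schedule steroid?**
- SAP 5.6: any-use count and a listing.
- SAP 7.1: SB-913 only.
- SAP 7.2.5: the adverse event tables have no row for steroid treatment. How an event was treated appears only in the listing.
- SAP 7.3: liver summaries and per-subject figures, with no steroid overlay stated.
- SAP 7.10: ACTH stimulation results are listed only.
- Protocol section 13: nothing on steroid dose, duration or departure from the taper.

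So none does.

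**2. What can the planned row show?** Let n be the cohort size and k the number with an increase, prolongation or restart. The planned class row is n/n for every k. The informative count is k/n.
- n = 2: the planned row is 2/2 (100%). The informative count is 0/2, 1/2 or 2/2.
- n = 4 (after expansion): the planned row is 4/4 (100%). The informative count runs from 0/4 to 4/4.

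The exact 95% upper limit for 0/n is 1 − 0.025^(1/n). This is 1 − 0.158 = 84.2% for n = 2 and 1 − 0.398 = 60.2% for n = 4. By symmetry the lower limit for n/n is 15.8% and 39.8%. Even 0/2 against 2/2 therefore gives overlapping intervals (0 to 84.2% and 15.8 to 100%).

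**3. Which liver findings could be missed or blunted in the existing summaries?**
- Protocol 10.1.1 counts a laboratory abnormality needing medication as an adverse event. Protocol 10.3 asks for Grade 1 or 2 laboratory abnormalities only if judged clinically significant. A low-grade rise may go unreported, and a held taper need not create an event at all.
- The steroid trigger is relative to Baseline, whereas shift tables are relative to the normal range. Illustration, assuming an upper limit of normal of 40: ALT moving from 15 to 32 is a 32/15 = 2.1-fold rise, which passes the trigger but shows no shift.
- Liver panels are drawn twice weekly to Week 20 (Protocol 9.13). When several values fall in one visit window, SAP 4.3 summarises the one closest to the protocol visit. A short, treated peak can drop out of the tables.

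**4. How far can exposure vary behind the same 100%?** The Appendix 3 schedule for a subject of 60 kg or more, with Day 0 counted outside Week 1, is:

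3×60 + 7×60 + 7×30 + 14×7×15 + 3×7×5 = 180 + 420 + 210 + 1,470 + 105 = 2,385 mg.

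The documents give no dose for an increase. As an assumption for illustration only, take one week at the schedule's own starting level of 60 mg/day. The added amount is (60 − scheduled daily dose) × 7:
- in Week 2: 30×7 = 210 mg, 210/2,385 = 8.8%
- in any one of Weeks 3–16: 45×7 = 315 mg, 13.2%
- after the course has ended: 60×7 = 420 mg, 17.6%

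The reference schedule itself differs between the documents. The first column covers Day -2 to Day 0 in Protocol Appendix 3 and Day -2 to Day 1 in SAP Appendix C. At 60 kg or more, if Day 1 were counted in addition to a full Week 1, the total would rise by 60 mg, or 60/2,385 = 2.5%.

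**The case against.** A reader might infer that the dose-related part of the main harm is absent from the summary tables. The documents do not support that. A liver-enzyme rise treated with extra prednisone fits the adverse event definition in Protocol 10.1.1, and SAP 7.2.5 tabulates such events by cohort, term, highest grade and relationship. If both subjects in a high-dose cohort and neither in a low-dose cohort were escalated for ALT, the event rows should also read 2/2 against 0/2. Steroid harms that occur are adverse events too.

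Masking is also limited. Extra steroid for transaminitis follows a rise in enzymes, and SAP 7.3 plots the liver panel for each subject and lists all laboratory data. The medication listing and the treatment field in the adverse event listing let cohorts of 2 to 4 be read by hand. Protocol 12.3 has the Safety Monitoring Committee evaluate all data in a triggered review.

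Most of this stands, and it narrows the point. It does not remove it: none of these outputs summarises the steroid response by dose, and the cases in part 3 of the working can escape the event tables or be blunted in the ALT tables.

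Two other readings go too far. It is not true that every named steroid will show 100%: the protocol allows an equivalent, so preferred-name rows may split, although no such row would identify an increase or restart. Nor does an extra week always add 18%. That figure needs an assumed 60 mg/day given after the course has ended.

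**Conclusion.** The concern holds as a reporting gap of modest size. For corticosteroids as a class, the any-use count carries no information on dose because it is about 100% in every cohort by design, and no planned table shows increase, prolongation or restart. The underlying liver events and the individual records remain available in other outputs.

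This rests on three assumptions: dosed subjects receive the mandatory prophylaxis; the steroids used fall in one ATC Level 4 group; and a table is wanted because the SAP sets out to display safety by dose. Any pattern would be descriptive, as the intervals above show. The point concerns reporting only and implies nothing about which steroid regimen is appropriate.

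**What to change.** 1. Reconcile the first column of the taper schedule between Protocol Appendix 3 and SAP Appendix C, so that off-schedule has a single reference.
2. In SAP 5.6 or 7.1, add a by-cohort count and percentage of subjects with any steroid increase above the scheduled taper, continuation past its planned stop, or restart after it.
3. Where dose and dates are captured, add days on steroid and cumulative prednisone-equivalent dose for each subject, with a matching exception in SAP 4.7, which at present rules out derivations.
4. Mark steroid changes on the per-subject liver figures already planned in SAP 7.3.

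The cost is SAP wording, one small table, some programming and a rule for converting equivalents. No change to treatment or visits is involved. One condition should be checked first: Protocol 7.2 and 9.3 do not say that the medications page holds steroid dose and start and stop dates, whereas Protocol 9.32 does specify dates and times for enzyme replacement infusions. If dose and dates are not captured, items 2 and 4 may need a manual review of subject records, and item 3 may not be possible.

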#### 6. ENDPOINT ANALYSIS

Since this is a single-dose study to evaluate safety, analyses will be descriptive and exploratory in nature. Change from the preceding year values may be calculated for selected clinical and laboratory parameters.

If there is a result with a "<" sign, will drop the sign and use half of the number for analysis. If the result is below detection limit, it will be imputed to half of detection limit in table and figure. The result will be listed as is in listings.

### 6.1 Primary Endpoint and Analysis

The primary endpoint of this study is the safety and tolerability of SB-913. Safety assessments are detailed in Section 7 of this SAP.

#### 6.2 Secondary Endpoints and Analyses

Secondary endpoints will be summarized by presenting descriptive statistics of actual values and changes from baseline at each visit, where applicable. The secondary endpoints consist of the changes from baseline over time in the following assessments:

- IDS activity measured in plasma
- Assessments will be conducted at Screening, Baseline, Weeks 2, 4, 6, 8, 12, 16, 20, 24, 36, 48, Months 15, 18, 21, 24, 27, 30, 33, 36/End of Study (EOS), and at any Early Termination Visit. Total GAG, dermatan sulfate (DS) GAG, and heparin sulfate (HS) GAG levels measured in urine

At each sampling time point, the actual value and the change from baseline for IDS activity and urine GAG levels will be summarized using descriptive statistics and plotted over time by treatment cohort.

For subjects who undergo ERT withdrawal, changes from pre- to post- ERT withdrawal in the frequency and dose of ERT infusions will be evaluated and summarized using monthly, quarterly, and annualized total dose and number of infusions. Duration of ERT withdrawal may also be analyzed. The ERT withdrawal period is defined as the date recorded on the ERT Withdrawal Trigger CRF form to the first date after ERT withdrawal recorded on the ERT administration.

• AAV2/6 clearance measured by vector genomes in plasma, saliva, urine, stool, and semen by PCR

AAV2/6 clearance measured by vector genomes in the different samples will be plotted over time by treatment cohort.

CONFIDENTIAL Page 15 of 28

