	Laboratory data will be summarized for each time-point at which specimens are collected. Change-from-Baseline values may be calculated for selected laboratory parameters. Shift-tables (Change-from-Baseline relative to the normal range) may be constructed for selected laboratory parameters.			

Secondary Analyses

At each sampling time point, the actual value and the change from baseline for IDS activity and urine GAG levels will be summarized using descriptive statistics and plotted over time by treatment cohort.

For subjects who undergo ERT withdrawal, changes from pre- to post- ERT withdrawal in the frequency and dose of ERT infusions will be evaluated and summarized using annualized total dose and number of infusions. Duration of ERT withdrawal may also be analyzed.

AAV2/6 clearance measured by vector genomes in the different samples will be plotted over time by treatment cohort.

ABBREVIATIONS

AAV	adeno-associated virus
AAV2/6	adeno-associated virus serotype 2/6
ACTH	adrenocorticotropic hormone
AE	adverse event/experience
AFP	α-fetoprotein
ALT	alanine aminotransferase (SGPT)
ANOVA	analysis-of-variance
AR	adverse reaction
AST	aspartate aminotransferase (SGOT)
BSC	BioSafety Committee
BSID-III	Bayley Scales of Infant Development
CNS	central nervous system
CRF	case report form
CSF	cerebrospinal fluid
CTCAE	Common Terminology Criteria for Adverse Events
DLT	dose-limiting toxicity
DNA	deoxyribonucleic acid
DS	dermatan sulfate
DSB	double-strand break
ECG	electrocardiogram
ECHO	echocardiogram
eCRF	electronic CRF
ELISA	enzyme linked immunoassay
EOS	End of Study
ERT	enzyme replacement therapy
ETV	early termination visit
FDA	Food and Drug Administration
FIX	Factor IX
FSHD	facioscapulohumeral muscular dystrophy
GAG	glycosaminoglycan
HBV	hepatitis B virus
HCC	hepato-cellular carcinoma
HCV	hepatitis C virus
HDR	homology-directed repair
HEENT	head, eyes, ears, nose, and throat
hFIX	human Factor IX
HIV	human immunodeficiency virus
hIDS	human IDS
HS	heparan sulfate
IAR	infusion-associated reaction
IATA	International Air Transport Association
ICH	International Council for Harmonisation
IDS	iduronate-2-sulfatase
IEC	institutional ethics committee
IKB	institutional review board

ITR	inverted terminal repeat
IV	intravenous
JROM	joint range of motion
LDH	lactate dehydrogenase
LTFU	long-term follow-up
MedDRA	Medical Dictionary for Regulatory Activities
MHRA	Medicines and Healthcare Products Regulatory Agency
MPS II	Mucopolysaccharidosis II
MRI	magnetic resonance imaging

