13.5 Secondary Endpoints

The following are secondary endpoints for this study:

- Change from Baseline in:
 - IDS activity measured in blood.
 - $\circ~$ Total GAG, DS GAG, and HS GAG levels (expressed as ratio to creatinine) measured in urine.
 - Monthly and annualized frequency and dose of idursulfase (or equivalent ERT).
- AAV2/6 clearance measured by vector genomes in plasma, saliva, urine, stool, and semen by PCR.

At each sampling time point, the actual value and the change from baseline for IDS activity and urine GAG levels will be summarized using descriptive statistics and plotted over time by treatment cohort.

For subjects who undergo ERT withdrawal, changes from pre- to post- ERT withdrawal in the frequency and dose of ERT infusions will be evaluated and summarized using monthly, quarterly, and annualized total dose and number of infusions. Duration of ERT withdrawal may also be analyzed.

AAV2/6 clearance measured by vector genomes in the different samples will be plotted over time by treatment cohort.

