# 4.2 Analysis Sets

All subjects enrolled in this study who receive any portion of the SB-913 infusion will be included in the Safety Analysis Set . All analyses (i.e., safety, primary, secondary, and exploratory) will be performed using the Safety Analysis Set .

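### ERT use is an unrestricted secondary endpoint, but its only specific analysis covers optional withdrawers, and subjects who never resume ERT have no defined withdrawal duration

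*SAP*

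**What the plan says.** Protocol 13.5 lists, under change from Baseline, "Monthly and annualized frequency and dose of idursulfase (or equivalent ERT". SAP 2.2.2 carries the same measure as its own bullet. Neither names a subgroup. Protocol 9.32 has every ERT dose logged from Screening so that frequency can be compared before and after SB-913.

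The analysis text is narrower. SAP 6.2 reads: "For subjects who undergo ERT withdrawal, changes from pre- to post- ERT withdrawal in the frequency and dose of ERT infusions will be evaluated", with results "summarized using monthly, quarterly, and annualized total dose and number of infusions". Protocol 13.5 has the same restriction. So does the protocol synopsis, where the result is "summarized using annualized total dose and number of infusions".

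Two general statements reach further. SAP 6.2 opens with "Secondary endpoints will be summarized by presenting descriptive statistics of actual values and changes from baseline at each visit, where applicable", and SAP 4.2 says "All analyses (i.e., safety, primary, secondary, and exploratory) will be performed using the Safety Analysis Set".

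On duration, SAP 6.2 says "Duration of ERT withdrawal may also be analyzed", and the "ERT withdrawal period is defined as the date recorded on the ERT Withdrawal Trigger CRF form to the first date after ERT withdrawal" found in the ERT administration record. Protocol 11.4 makes withdrawal optional, opens it at 12 weeks after dosing to willing and medically stable subjects, lets ERT stay off after the Follow-Up visit, and allows repeat attempts after an unsuccessful one.

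**The concern.** The stated endpoint concerns ERT use after SB-913 in the trial's subjects. The specified analysis concerns ERT use after withdrawal, in those who withdrew. These differ in population and in time origin. The withdrawers are chosen after treatment by investigator judgement and subject willingness, so a reduction among them says little about ERT use across everyone dosed.

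The duration definition has a separate gap. Staying off ERT is the outcome that the treatment aims for, yet it is the one outcome for which the definition yields no value. A summary of the durations that do exist would describe only subjects who went back on ERT.

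**Working it through.** The documents give no ERT rate or duration to reproduce. The only related figure is enrolment: 8 cohorts x (2 + about 2) = 32, so a cohort has 2 to about 4 subjects. ERT inputs below are assumptions.

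**1. Does any text give ERT rates in all dosed subjects?**

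- SAP 6.2 lead-in: a per-visit summary where applicable, with no ERT rate defined.
- SAP 4.2: names the population, not a summary.
- SAP 4.3: baseline is the last pretreatment value (a mean for GAG/IDS). Neither is a baseline infusion rate.
- SAP 4 listings: by-subject data, no rates.
- SAP 5.6: number and percent using each concomitant medication, not infusions or dose.

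None supplies the rate that the endpoint names.

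**2. Subset versus all dosed.** Assume that k of n subjects stop completely and the rest do not change. The withdrawer mean change is -100%; the all-subject mean change is -100% x k/n. For k = 1 and n = 4, that is -25%.

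**3. Annualized rate and observation period.** Assume weekly ERT (52/year), stopped at Week 12, with d weeks off and P weeks observed from the stop date. Post rate = (P - d)/P x 52; reduction = d/P. Week 52 gives P = 52 - 12 = 40. Month 36 (156 weeks) gives P = 156 - 12 = 144.

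| Post period | P (weeks) | Post rate, d = 8 | Reduction, d = 8 | Reduction, d = 4 to 12 |
|---|---|---|---|---|
| Withdrawal period itself | d | 0 | 100% | 100% |
| 12 weeks (latest Follow-Up visit) | 12 | 17.3/year | 66.7% | 33.3% to 100% |
| To Week 52 | 40 | 41.6/year | 20.0% | 10.0% to 30.0% |
| To Month 36 | 144 | 49.1/year | 5.6% | 2.8% to 8.3% |

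The first row applies only if the withdrawal period is taken as the post window. On the pre side, if the window is the 12 weeks after SB-913 and one infusion falls in the ERT-free interval of protocol 3.5 (number assumed), the rate is 11/12 x 52 = 47.7/year.

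**4. Duration.** A subject who stops at Week 12 and never resumes has no value as defined. The time observed off ERT is 40 weeks on leaving at Week 52 for the Long-term Follow-Up Study (protocol 3.4), or 144 weeks at Month 36. Earlier exit, allowed case by case, would shorten it.

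Now assume four subjects who stop at Week 24, so 156 - 24 = 132 weeks remain. Two resume at 8 and 12 weeks and two never do. The mean of the defined durations is (8 + 12)/2 = 10 weeks. Counting observed time for the other two gives (8 + 12 + 132 + 132)/4 = 71 weeks, a lower bound. SAP 4.5 covers only results below the detection limit, so no censoring rule fills the gap.

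**The case against.** **The restriction looks deliberate.** SAP 6.2 follows the analysis text of protocol 13.5, and protocol 3.5 keeps non-withdrawers on their schedule, so little change is expected in them. A reader might infer that the SAP departs from the protocol here. It does not: the mismatch lies within the protocol too, between its endpoint and its analysis. A reader might also infer that an all-treated table would show the effect of SB-913. It would not, for the reason just given. That limits what the table means, but the endpoint as written still goes unreported.

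**Other text already covers everyone.** With 2 to about 4 subjects per cohort, by-subject listings carry much of the information, and protocol 7.2 also records ERT as a concomitant medication. This stands as mitigation. It supplies no rates.

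**No ERT bullet after the SAP 6.2 lead-in proves little.** Agreed. The bullets there are out of order in the available text, and the point does not rest on them.

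**The rate figures are built on assumptions.** This largely stands. The SAP does not tie the withdrawal period to the rates, so the 100% row is one reading only. The 66.7% row needs resumption before the Follow-Up visit, which protocol 11.4 allows, although protocol 9.33 places the assessment at that visit. Monthly and quarterly totals carry their length in their names. The missing period is mainly a missing detail of the annualized rate.

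**Duration is optional, and nothing excludes non-resumers.** Correct. A reader might infer that the SAP chose to drop them. It is silent on their end date, so the bias arises only if the analysis is done on defined durations alone.

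**Conclusion.** The point holds in two parts. First, an unrestricted secondary endpoint has a specified analysis only in a subset selected after treatment, and nothing else in either document yields ERT rates in all dosed subjects. Second, if duration is analysed, non-resumers have no defined value and a summary of defined durations would be biased short.

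The size depends on unknown ERT behaviour. The -100% versus -25% contrast, the 5.6% to 100% range for an 8-week gap and the 10 versus 71 weeks are illustrations under assumed weekly ERT or assumed stop and resumption times, not predictions. The study is descriptive, so no test, error rate or power is at issue, and the primary safety endpoint is untouched. What changes is what this one secondary endpoint reports. It is worth settling before the analysis, because with so few subjects the choice of subset and period could largely decide the result.

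**What to change.** 1. **ERT use.** In SAP 6.2, reconciled with protocol 13.5 and the synopsis, add a descriptive summary of ERT infusions and total dose per unit of observed time, before versus after SB-913, in all dosed subjects on ERT at entry. Take it from the ERT log, and state how the ERT-free interval around infusion (protocol 3.5) is handled. Say that it describes ERT use and does not isolate an SB-913 effect. Keep the pre/post-withdrawal summary, labelled as a selected subset, and state the pre and post observation periods behind its annualized rate.

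2. **Duration, if reported.** Censor subjects who have not resumed at the last visit at which the ERT log was confirmed. Treat each withdrawal attempt as its own episode. List every episode by subject with a censoring flag. Summarise with a method that allows censoring, such as Kaplan-Meier, or give the number still off ERT with the time observed.

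**Cost.** SAP wording, a matching protocol clarification and a little extra programming on data already collected; clinical management does not change. The all-treated summary will probably show a smaller reduction than the withdrawer summary.
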